3.2 Subject Exclusion Criteria

The subject must be excluded from participating in the trial if the subject:

3.2.1 *Is currently participating and receiving study therapy or has participated in a study of an investigational agent and received study therapy or used an investigational device within 4 weeks of the first dose of treatment.*

3.2.2 *Has a diagnosis of immunodeficiency or is receiving systemic steroid therapy or any other form of immunosuppressive therapy within 7 days prior to the first dose of trial treatment.*

3.2.3 *Has a known history of active TB (*Bacillus Tuberculosis*).*

3.2.4 *Hypersensitivity to pembrolizumab or any of its excipients. History of hypersensitivity to other antibodies can be discussed with the PI to determine eligibility.*

3.2.5 *Has had a prior anti-cancer monoclonal antibody (mAb) within 4 weeks prior to study Day 1 or who has not recovered (i.e., \leq Grade 1 or at baseline) from adverse events due to agents administered more than 4 weeks earlier.*

3.2.6 *Has had prior chemotherapy, targeted small molecule therapy, or radiation therapy within 2 weeks prior to study Day 1 or who has not recovered (i.e., \leq Grade 1 or at baseline) from adverse events due to a previously administered agent.*

Note: Subjects with \leq Grade 2 neuropathy are an exception to this criterion and may qualify for the study.

Note: If subject received major surgery, they must have recovered adequately from the toxicity and/or complications from the intervention prior to starting therapy.

- 3.2.7 *Has experienced an immune-related adverse event requiring discontinuation of a prior checkpoint inhibitor.*
- 3.2.8 *Has a known additional malignancy that is progressing or requires active treatment. Exceptions include basal cell carcinoma of the skin or squamous cell carcinoma of the skin that has undergone potentially curative therapy or in situ cervical cancer.*
- 3.2.9 *Has known active central nervous system (CNS) metastases and/or carcinomatous meningitis. Subjects with previously treated brain metastases may participate provided they are stable (without evidence of progression by imaging for at least four weeks prior to the first dose of trial treatment and any neurologic symptoms have returned to baseline), have no evidence of new or enlarging brain metastases, and are not using steroids for at least 7 days prior to trial treatment. This exception does not include carcinomatous meningitis which is excluded regardless of clinical stability.*
- 3.2.10 *Has active autoimmune disease that has required systemic treatment in the past 2 years (i.e. with use of disease modifying agents, corticosteroids or immunosuppressive drugs). Replacement therapy (e.g., thyroxine, insulin, or physiologic corticosteroid replacement (such as prednisone 10mg daily or its equivalent) for adrenal or pituitary insufficiency, etc.) is not considered a form of systemic treatment.*
- 3.2.11 *Has known history of, or any evidence of active, non-infectious pneumonitis.*
- 3.2.12 *Has an active infection requiring systemic therapy.*
- 3.2.13 *Has a history or current evidence of any condition, therapy, or laboratory abnormality that might confound the results of the trial, interfere with the subject's participation for the full duration of the trial, or is not in the best interest of the subject to participate, in the opinion of the treating investigator.*
- 3.2.14 *Has known psychiatric or substance abuse disorders that would interfere with cooperation with the requirements of the trial.*
- 3.2.15 *Is pregnant or breastfeeding, or expecting to conceive or father children within the projected duration of the trial, starting with the pre-screening or screening visit through 120 days after the last dose of trial treatment.*
- 3.2.16 *Has a known history of Human Immunodeficiency Virus (HIV) (HIV 1/2 antibodies).*
- 3.2.17 *Has known active Hepatitis B (e.g., HBsAg reactive) or Hepatitis C (e.g., HCV RNA [qualitative] is detected).*

3.2.18 Has received a live vaccine within 30 days of planned start of study therapy.

Note: Seasonal influenza vaccines for injection are generally inactivated flu vaccines and are allowed; however intranasal influenza vaccines (e.g., Flu-Mist®) are live attenuated vaccines, and are not allowed.

Patients with a condition requiring systemic treatment with either corticosteroids (>10 mg daily prednisone equivalent) or other immunosuppressive medications within 14 days of randomization. Inhaled or topical steroids and adrenal replacement steroid doses ≤ 10 mg daily prednisone equivalent, are permitted in the absence of active autoimmune disease.

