12.9 Case Report Forms

Patient medical information obtained by this study is confidential, and disclosure to third parties other than those noted below is prohibited.

Upon the patient's permission, medical information may be given to his or her personal physician or other appropriate medical personnel responsible for his or her welfare. This medical information must be made available to Oncologie and authorized representatives of Oncologie, upon request, for source verification of study documentation.

Data generated by this study must be available for inspection upon request by representatives of the U.S. FDA, local health authorities, Oncologie, Inc., and their authorized representative(s), collaborators and licensees, and the IRB for each study site, if appropriate.

All information will be collected on study-specific case report forms in CRMS by the study staff.

The completed forms will be forwarded for central review and inclusion in the study dataset with relevant source documentation as outlined in the case report forms. The data submission schedule is as follows:

At the time of registration:

- a. Registration Form
- b. Informed Consent Form (signed by the subject)
- c. Eligibility Checklist
- d. Source documents related to eligibility and randomization

Within 2 weeks after registration:

- a. Baseline study case report forms
- b. Pertinent source documents

Within 2 weeks after final dose of study medication:

- a. On study case report forms
- b. Pertinent source documents

The investigator will permit study-related monitoring, audits, and inspections by the IRB, government regulatory bodies, and University compliance and quality assurance groups of all study related documents. The investigator will ensure the capability for inspections of applicable study-related facilities (e.g. pharmacy, diagnostic laboratory, etc.).

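### Eligibility wording: the albumin limit is in the wrong unit, 3.2.2 cancels the replacement-steroid permission in the last exclusion, and a 14-day window runs from a randomization that never happens

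*Combined protocol and SAP*

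**What the plan says.** **Albumin.** The laboratory table in 3.1.7 requires albumin of at least 2.5 mg/dL. Hemoglobin in the same table is given in g/dL (at least 9).

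**Steroids.** Criterion 3.2.2 excludes a patient who "is receiving systemic steroid therapy or any other form of immunosuppressive therapy within 7 days prior to the first dose of trial treatment". It states no dose threshold and no exception for replacement. The last, unnumbered exclusion in 3.2 is aimed at doses above 10 mg/day prednisone equivalent. It adds that inhaled or topical steroids and "adrenal replacement steroid doses ≤ 10 mg daily prednisone equivalent, are permitted in the absence of active autoimmune disease". Criterion 3.2.10, on autoimmune disease, says that replacement therapy, with a physiologic corticosteroid dose among its examples, "for adrenal or pituitary insufficiency, etc.) is not considered a form of systemic treatment".

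**Anchor.** The last exclusion applies to corticosteroids above that dose "or other immunosuppressive medications within 14 days of randomization". The front-page summary describes a single-arm study. Other windows in 3.2 use other anchors: 3.2.1 counts "within 4 weeks of the first dose of treatment", and 3.2.6 counts "within 2 weeks prior to study Day 1". Section 12.9 lists "Source documents related to eligibility and randomization" among the items due at registration. Section 5, after the trial-treatment table, requires treatment to begin within 14 days of registration.

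**The concern.** Eligibility criteria are applied one patient at a time, from a checklist, by staff who should not have to guess what was meant. Here one limit has no effect if followed literally, one pair of criteria can give opposite answers for the same patient, and one window has no defined starting point.

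The steroid question is foreseeable. Every patient must have progressed on a checkpoint inhibitor (3.1.1). The protocol lists hypophysitis among pembrolizumab toxicities and lets pembrolizumab continue during endocrine replacement (5.2.2, Table 3). Criterion 3.2.7 excludes only immune-related events that forced discontinuation of the prior inhibitor. A patient with earlier, managed hypophysitis could therefore arrive on replacement steroids. The documents give no frequency, and none is assumed here.

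What is at stake is consistent enrolment, not the statistical test.

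**Working it through.** **1. Albumin unit.** 1 g = 1000 mg, so 2.5 mg/dL = 2.5 / 1000 = 0.0025 g/dL. The evident limit is 2.5 g/dL, and 2.5 / 0.0025 = 1000. A literal limit of 0.0025 g/dL excludes nobody.

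**2. Replacement steroids.** Take a patient on 5 mg/day prednisone equivalent for adrenal insufficiency, with no active autoimmune disease.

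- Last exclusion: 5 is at or below 10, so the patient is expressly permitted.
- 3.2.2, read literally: the patient takes a systemic steroid within 7 days of first dose, so the patient is excluded.
- Exclusions are cumulative, so a strict reader lets 3.2.2 govern. But replacement is normally continuous, so 3.2.2 would then catch essentially every patient whom the adrenal permission covers, and the permission would do nothing.
- Two pieces of text point the other way. 3.2.2 groups the barred steroids with other forms of immunosuppression, and replacement need not be immunosuppression. 3.2.10 says that replacement does not count as systemic treatment, although that sentence sits inside the autoimmune criterion and does not amend 3.2.2.

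The permissive reading is therefore the likelier one, but 3.2.2 does not state it.

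**3. Anchor of the 14-day window.** Let d be the days from registration to first dose.

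- Counted from first dose, the window reaches back 14 days before first dose.
- Counted from registration, it reaches back 14 + d days before first dose.
- The two readings disagree only when the last disqualifying dose falls between day -(14 + d) and day -14, a band d days wide.

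The range of d:

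- Section 5 alone allows d = 0 to 14.
- Screening labs must fall within 10 days before treatment starts (3.1.7 and Section 9), and the 3-day leeway in Section 9 does not extend to screening evaluations. The eligibility checklist and its source documents are due at registration (12.9). If the labs that support registration are to stay valid at first dose, d is at most 10.
- So d is normally 0 to about 10, and the registration reading reaches 14 to 14 + 10 = 24 days before first dose. Going to d = 14, and so to 28 days, requires repeat labs.

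Illustration with d = 10: the band runs from day -24 to day -14. A last 20 mg dose on day -20 is 20 - 10 = 10 days before registration, under 14, so the patient is excluded. It is 20 days before first dose, over 14, so the patient is allowed. Because 5.3.2 restricts systemic glucocorticoids during screening, this case arises only if screening began after day -20.

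**4. The primary test.** Section 11 continues after at least 1 response in 10 patients and rejects the null with at least 4 in 29. The exact binomial calculation gives a type I error of 0.0468 at a response rate of 5% and power of 0.801 at 20%. This reproduces the stated 5% and 80%. None of the three wording points enters that calculation.

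**The case against.** The strongest reply is that sensible staff would resolve all of this unaided. Nobody would apply an albumin limit of 0.0025 g/dL. The express permission, read with 3.2.10, shows that replacement is allowed. The word randomization is evidently left over from another text. Much of this stands: the first and third points are drafting slips, and on the second the two readings do not carry equal weight. It does not remove the need for correction. The albumin figure is an operative threshold that is simply wrong, and 3.2.2 on its face still excludes patients whom the last exclusion admits.

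A reader might go further than the documents allow in three ways.

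- *That 3.2.9 contains the same error.* It readmits patients with treated brain metastases only if they "are not using steroids for at least 7 days prior to trial treatment", with no replacement exception. That is a stricter condition for one subgroup and is compatible with a general permission. Nothing shows that an exception was intended there.
- *That the 7-day and 14-day steroid windows contradict each other.* They do not. A bar on any systemic steroid within 7 days and a bar on higher doses within 14 days can both apply.
- *That first dose is plainly the intended anchor.* The first-dose wording in 3.2.1 and 3.2.2 gives that some support. But Section 7.2 repeatedly pairs randomization with treatment allocation as a point after consent, and 12.9 places it at registration. The protocol's own usage is closer to registration.

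**Conclusion.** The concern holds as a minor one about eligibility criteria.

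- The albumin limit is wrong by a factor of 1000.
- The conflict between 3.2.2 and the last exclusion is real on a literal reading, although replacement was probably meant to be allowed.
- The randomization anchor is a clean-up item. The two candidate anchors normally differ by 0 to about 10 days, and by up to 14 only with repeat labs. This rests on the assumption that the labs supporting registration are the ones that must still be valid at first dose.

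The number of patients affected cannot be derived from the documents. A reader might infer that the response rate or the error rates are compromised. The documents do not support that: type I error, power and the response-rate test do not depend on any of these passages.

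**What to change.** 1. In the 3.1.7 laboratory table, change the albumin limit to at least 2.5 g/dL. Patients below that level become clearly ineligible.
2. Add to 3.2.2 an exception for adrenal replacement at or below 10 mg/day prednisone equivalent in the absence of active autoimmune disease. On a literal reading this slightly relaxes 3.2.2, so the sponsor should confirm it. If the sponsor wants the strict bar, delete the adrenal permission from the last exclusion instead. While editing, state whether pituitary replacement is covered, since 3.2.10 names it and the last exclusion does not. Leave 3.2.9 as it is.
3. In the last exclusion, replace randomization with registration. First dose is acceptable if the sponsor confirms the shorter look-back, normally shorter by 0 to about 10 days.

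The cost is protocol text and the sponsor's confirmation. No visits, tests or patients are added.

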3.3 Inclusion of Women and Minorities

Both men and women of all races and ethnic groups are eligible for this trial.

4. STUDY VISIT SCHEDULE AND PROCEDURES

4.1 Screening

See study table in Section 9 for screening procedures.

4.2 Treatment period

One cycle is 21 days. Patient will remain on treatment as long as they are obtaining clinical benefit with a PR, CR or SD as per RECIST 1.1 criteria, and are without significant toxicity requiring treatment discontinuation.

4.3 Post-Treatment Tumor Follow-up – Once treatment on protocol has discontinued, no further tumor assessments are necessary. The last obtained CT on protocol will be utilized for response assessments.

4.4 End-of-Treatment Visit – This will be planned if feasible within 2 weeks of discontinuation of therapy.

4.5 Long-Term Survival Follow-Up – patients will be followed for survival for 1 year after discontinuation of treatment. Review of medical records or phone calls would be sufficient.

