1.3 Secondary Endpoints

1.1.1 *Progression free survival*

Progression-free survival will be measured from the time of study enrollment until radiologic, clinical progression or death.

1.1.2 *Duration of response*

Time (time of first response until progression).

1.1.3 *Overall survival*

Overall survival will be measured from the time of enrollment until death.

1.1.4 *Safety and tolerability*

Toxicities observed in the study will be assessed by CTCAE 5.0 criteria.

1.1.5 *Laboratory correlates of response*

1.1.5.1 **PD-L1 expression pre and post treatment**

1.1.5.2 **Presence of TILs (tumor infiltrating lymphocytes) pre and post treatment**

1.1.5.3 **Assessment of immune markers in pre-treatment fresh and post-treatment biopsies and blood.**

1.1.5.4 **Assessment of genomics and tumor mutation burden in select patients.**

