5. TREATMENT PLAN

This phase II study will enroll patients who are eligible and those who sign consent will undergo screening, including acquisition of fresh tissue for correlative analyses, updated imaging and labs. Eligible patients will be enrolled and treated with bavituximab 3 mg/kg IV weekly and pembrolizumab 200mg IV every 3 weeks. One cycle is defined to be 21 days. Patients will be seen for assessments on day 1 of each cycle. Blood will be collected for PK and PD analyses at baseline and during cycles 1 and 2. Patients will be re-staged every 3 cycles and treatment will continue until progression, or significant toxicity up to 24 months. Fresh baseline tissue will be collected and repeat tumor biopsy will be obtained (if feasible) at a time-point week 4-6 after treatment start for correlative analyses. This on study biopsy should not proceed if tumor is inaccessible or if biopsy is not thought to be in the patient's best interest.

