9. STUDY CALENDAR

Baseline laboratory and exam evaluations are to be conducted within 10 days prior to start of protocol therapy. Scans and x-rays must be done \leq 4 weeks prior to the start of therapy. In the event that the patient's condition is deteriorating, laboratory evaluations should be repeated within 48 hours prior to initiation of the next cycle of therapy.

With the exception of screening evaluations, all time points on study have leeway of plus or minus 3 days.

	Pre-Study		3 week cycles (repeat)					EOS	Follow up
			Cycle 1	Cycle 2	Cycle 3	Cycle 4			
Pembrolizumab ¹			X	X	X	X			
Bavituximab ⁷			X	X	X	X			
Informed Consent	X								
History & Physical ²	X		X		X	X	X		
Concurrent Meds	X		X		X	X	X		
CBC and Chemistry ³	X		X			X			
Research Bloods ⁴	X		X		X	X	X	X	
β-HCG ⁸	X								
AE assessment	X		X		X	X	X		X
CT or MRI for Tumor Assessment ⁵	X ^{5*}						X ⁵		
Tumor Biopsy ⁶	X					X			
Review of medical records, telephone contact for recurrence-free and overall survival									Every 3 months up to 1 year

¹. 200 mg IV day 1 of each cycle up to 24 months while on study

². History to be collected only at baseline; physical, includes interval history, prior treatment and radiation exposure, vital signs, (heart rate, systolic and diastolic blood pressure, oxygenation at rest and walking, height, weight, and performance status. Height is only required at baseline.

³. Complete blood count and differential, and comprehensive metabolic panel, NOTE -TSH, Free T4 once every 4 weeks.

⁴. Amount is detailed in laboratory manual.

⁵. Tumor assessment includes radiologic assessment for RECISTv1.1 evaluation. Repeat radiologic assessment at week 9 and every 9 weeks thereafter while patient continues to receive study therapy.

⁶. Tumor biopsy to be obtained after cycle 4 if feasible. Archival tissue will be collected at baseline if pre-study biopsy is not feasible at the discretion of the PI.

⁷ Bavituximab is dosed weekly

⁸ See section 3.1.8

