11.1 Data Analysis

We will summarize the response experience of the patients with percentages and confidence intervals. (We will not adjust for the interim analysis when computing the confidence intervals.) We will define overall survival as the time from the start of treatment until death from any cause. Patients who leave the study and whose survival status we cannot determine will be censored at the last date they were known to be alive. Progression-free survival will be the time from the start of treatment until disease progression or death from any cause. Patients who start non-protocol therapy in the

absence of disease progression will be considered to have progressed on the date the new therapy begins. If the patient is lost to follow up, the patient's time to progression will be censored at the last date they were known to be alive and disease free. Duration of response will be defined as the time from the first known response until disease progression, with death not related to disease censoring this endpoint. All failure-time endpoints will be analyzed with appropriate statistical methods for censored data. We will estimate the distributions of times until the events by the method of Kaplan and Meier. We will fit the proportional hazards model to learn about associations of patient or tumor characteristics with failure-time endpoints. Data displays will include summary statistics and confidence intervals.

Correlative analyses (e.g., laboratory correlates of response, such as PD-L1 expression, presence of TILs, and changes in immune markers) will be exploratory

Safety Analysis

All patients who receive any study treatment will be included in final summaries of safety data. Summaries of AEs and other safety parameters will be provided as appropriate. Summary tables for extent of exposure to study treatment will also be provided.

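### Survival follow-up ends one year after each patient's own treatment stop, so the overall survival curve may be biased upward after about month 14; a common cut-off would remove this cheaply

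*Combined protocol and SAP*

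**What the plan says.** Section 4.5 states that "patients will be followed for survival for 1 year after discontinuation of treatment", and accepts record review or telephone calls as the means. The follow-up column of the study calendar (section 9) matches: "Every 3 months up to 1 year". The length of treatment sets the start of that year. Section 5 says "treatment will continue until progression, or significant toxicity up to 24 months", and a calendar footnote fixes the scans: "Repeat radiologic assessment at week 9 and every 9 weeks thereafter".

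Section 11.1 defines the endpoint: "We will define overall survival as the time from the start of treatment until death from any cause". For all failure-time endpoints, "We will estimate the distributions of times until the events by the method of Kaplan and Meier", and proportional hazards models are also fitted. The OS censoring rule in the same section is that people no longer in the trial "whose survival status we cannot determine will be censored at the last date they were known to be alive".

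I found no common survival cut-off date, no contact planned after the one-year window, no limit on how far the OS curve will be reported, and no sensitivity analysis for dependent censoring.

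**The concern.** Kaplan-Meier estimation assumes that patients censored at a given time have the same future risk as those still being followed. Administrative censoring at a calendar date usually meets this, because follow-up then depends on when a patient entered. Here follow-up depends on when the patient stopped treatment, and stopping is driven largely by progression. Survivors who stopped early leave the risk set first. The later part of the curve then rests increasingly on patients whose disease stayed controlled longest.

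OS is a secondary endpoint in section 1.3. Its late part is where a durable benefit of immunotherapy would be looked for, and it is the part this rule affects.

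**Working it through.** **The plan's own figures.** The documents state no OS figure. The design figures in section 11 concern response rate and reproduce exactly. With at least 1 response in 10 needed to continue and at least 4 in 29 to reject, P(reject) = Σ over x = 1 to 10 of P(X₁ = x) × P(X₂ ≥ 4 − x), where X₁ ~ Bin(10, p) and X₂ ~ Bin(19, p). This gives 0.0468 at p = 5% and 0.801 at p = 20%. Nothing in this calculation depends on survival follow-up.

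**Censoring time of a survivor.** Censoring time = time on treatment + 12 months (30.4 days per month):

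- Stop at the week-9 scan: 63/30.4 = 2.1, so month 14.1.
- Stop after progression is confirmed 4 to 8 weeks later (section 10): 91/30.4 = 3.0 to 119/30.4 = 3.9, so month 15.0 to 15.9.
- Stop at the 24-month maximum: month 36.

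The rule censors nobody before month 12. Only stops before the first scan, for toxicity or clinical progression, bring censoring nearer to month 12 than to month 14. The time origin differs between section 1.3 ("Overall survival will be measured from the time of enrollment until death") and section 11.1. Treatment must start within 14 days of registration, so if enrollment means registration the difference is at most 14/30.4 = 0.5 month and does not matter here.

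**Size of the bias.** This needs inputs that the documents do not give. An illness-death model was simulated with 400,000 patients per scenario: progression detected at 63-day scans, treatment capped at 24 months, survivors censored 12 months after stopping. Assumptions:

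- median time to progression 2 to 3 months (12 months for an assumed 10% who respond);
- median survival after progression 3 to 10 months;
- shared gamma frailty variance 0 to 1;
- on-treatment death hazard 0.01 per month.

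Selected scenarios, each cell showing true value / Kaplan-Meier value:

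| Median months to progression; after progression; frailty variance | OS at 18 mo, % | OS at 24 mo, % | Median OS, mo | Censored of 29 |
|---|---|---|---|---|
| 2; 3; 0 | 8.8 / 9.6 | 4.0 / 5.5 | 7.23 / 7.25 | 1.7 |
| 2; 5; 0 | 18.5 / 19.5 | 9.3 / 12.3 | 9.38 / 9.40 | 5.2 |
| 2; 5; 0.5 | 32.4 / 34.0 | 23.7 / 27.9 | 11.11 / 11.15 | 8.3 |
| 3; 6; 0.5 | 39.7 / 41.0 | 29.9 / 33.9 | 13.67 / 13.70 | 9.6 |
| 2; 8; 0.5 | 43.1 / 45.1 | 33.2 / 38.7 | 14.87 / 15.05 | 12.1 |
| 3; 10; 0.5 | 50.9 / 52.6 | 40.7 / 45.8 | 18.47 / 20.00 | 13.7 |

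True and estimated OS agree at month 12 in every scenario, and at month 14 wherever it was tabulated. Over all scenarios the excess is 0.7 to 2.0 points at 18 months and 1.5 to 5.8 points at 24 months (largest: 41.5% against 47.3%). At 36 months it reaches 44.3 − 35.1 = 9.2 points under the strongest frailty.

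**A second model.** Assume 20% of patients with median OS 30 months and median treatment 12 months, and 80% with 8 and 2.5 months. OS at 24 months is then 21.6% true against 26.4% estimated, and 43.5% on both at 12 months. Adding 2 months to treatment, to represent stopping only after confirmation, cuts the 24-month excess from 4.8 to about 3.5 points and the 18-month excess from 1.9 to 0.8.

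**Two controls.** If survival is unrelated to time on treatment, the bias vanishes (24-month OS 18.8% true, 18.7% estimated). With a common cut-off 12 months after last enrolment and an assumed uniform 24-month accrual, Kaplan-Meier agrees with true OS within 0.1 point at 12, 18, 24 and 30 months.

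**Sampling error.** √(p(1 − p)/29), ignoring censoring, is 7.4 points at p = 20%, 8.5 at 30% and 9.1 at 40%.

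**The case against.** The strongest case against is that little in this trial rests on late OS. The documents set no 18- or 24-month landmark, no OS hypothesis and no OS decision rule. The trial has at most 29 patients, or 10 if it stops after stage 1. In the two-group model rerun at 29 patients, the 24-month estimate has a standard deviation of about 11 points, with fewer than 2 patients at risk on average. This stands, and it limits the weight of the point. It does not remove it: the bias would not shrink with more patients, confidence intervals do not reflect it, and the thin risk set is partly the rule's own effect.

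Second, section 11.1 censors only patients whose status cannot be determined, so later dates found in records could be used. That is allowed but not planned, and chance use would be uneven across patients.

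Third, the onset depends on when treatment stops. Section 4.2 ties treatment to continued response or stable disease. Section 4.6.8 lists confirmed progression as the reason to stop, and section 10 allows treatment until confirmation. These passages must be reconciled. Either way, censoring still depends on time on treatment; only its earliest date moves.

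A reader might also infer that the proportional hazards models in section 11.1 are biased. This was not shown. They need independent censoring given the covariates, and no hazard-ratio bias was computed.

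**Conclusion.** The follow-up rule makes OS censoring depend on time on treatment; this follows from the text alone. That it pushes the curve upward is conditional: patients who stop early must have a higher later death risk than those still followed. This is plausible, but the documents do not quantify it. Under the assumed inputs, the excess starts at about month 14 and is roughly 1 to 2 points at 18 months and 1.5 to 6 at 24 months, below the sampling error at those times.

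Three stronger readings are not supported. The curve is not shown to be wrong from month 12, since no scheduled progression stop leads to censoring before about month 14. The median is not generally overstated: it moves appreciably only when the true median lies beyond about 14 months (18.5 against 20.0 months in one scenario). The trial's main conclusion is not at risk, because it rests on response rate. This is a cheap improvement to a secondary endpoint, not a flaw in the design.

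**What to change.** Amend section 4.5 and the calendar so that every patient is followed for survival to death or one common calendar cut-off, whenever that patient stopped treatment; for example, 12 months after the last patient stops. State in section 11.1 that survivors are censored at that cut-off, or at the date last known alive if truly lost to follow-up. Use one OS time origin in sections 1.3 and 11.1 in the same amendment.

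The cost is a few extra record checks or calls for surviving early stoppers among at most 29 patients, with no added visits or scans. Section 4.7 already keeps the study open until survival follow-up is no longer needed, so the example cut-off adds no study time if the last patient to stop survives the year.

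If this is not adopted, show numbers at risk under the OS curve, and do not interpret it beyond about 12 to 14 months without a dependent-censoring sensitivity analysis, such as inverse-probability-of-censoring weighting.
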